6.2.2 Masking

This will be an investigator-masked clinical study. The **first ophthalmologist investigator** will remain masked to the IMD. He will NOT dispense or receive the returned IMD from the patients.

Masking will be achieved by providing the 2 IMD (T2259 and Vismed® multi) in identical cardboard and by identifying each IMD by a treatment number.

The **second ophthalmologist** investigator will be in charge of IMD dispensation, accountability and of patient questioning.

The code should not be broken except:

- In case of a medical emergency (where knowledge of the IMD received would affect the treatment of the emergency);
- Or when it is a regulatory requirement.

If an emergency code breaking becomes necessary, the investigator should notify the Sponsor, if possible, prior to breaking the code. The investigator and/or pharmacist are responsible for accessing the Interactive Web Response System to obtain the identity of the IMD allocated to the patient. When a code is broken, the date, time and reason must be recorded in the patient's source documentation as well as in the e-CRF, and in any associated AE report. The identity of the IMD should not be disclosed in these documents.

Further to a USADE assessment by the Global Drug Safety & Medical Information Department, the code might be broken for reporting purposes. The relevant Laboratoires Théa, CRO, and investigator staff remains unaware of the identification of the IMD.

The overall randomisation list will be broken only for data analysis after database lock.

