6 DESIGN OF THE CLINICAL INVESTIGATION

6.1 General

The chosen methodology and criteria correspond to the standard usually used in the recent clinical trials in DES (HAS Optive, 2011).

Thus, this is a multicentre, randomized, investigator-masked, two parallel groups (T2259 versus Vismed® Multi) investigation in dry eye patients with superficial keratitis. The investigation will be performed in France, in Spain, in Slovakia and in Poland.

Multicenter (and multi-investigator) design will provide the possibility of recruiting the subjects from a wider population and of using the device in a broader range of clinical settings, thus presenting an experimental situation that is more typical of future use. In this case, the involvement of a number of investigators also gives the potential for a wider range of clinical judgment concerning the value of the therapeutic intervention. In addition, it is also a practical mean of accruing sufficient subjects to satisfy the study objective within a reasonable timeframe.

Because of a different visual aspect of the tested eye-drops, a double-masked comparison is not possible. Thus an investigator-masked method will be used. The identity of the IMD provided to each patient and the data concerning the instillation schedule will not be known by the investigator in charge of the examinations and of performance and safety assessments. The two different treatment units will be identical in external appearance in order to respect the randomisation. A second investigator (a physician) will dispense medications allowing to mask the first ophthalmologist investigator (who will be in charge of all examinations and assessments), and patients will be instructed not to disclose drug information with other staff members or the first investigator.

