Visit #2 will take place 7 to 10 days after the selection visit (visit #1) and will consist of the following procedures and examinations (to be done according to the following order and in **each eye** for ocular assessments).

By **the first investigator** in charge of all examinations and safety assessment during the investigation:

- Questioning about Hydrabak® compliance during the run-in period;
- Questioning about concomitant ocular and non-ocular treatments;
- Questioning about AEs during the run-in period;
- Measurement of OSDI score;
- Questioning about ocular symptoms;
- Measurement of conjunctival hyperaemia with McMonnies photographic scale;
- Slit lamp examination for measuring:
 - TBUT,
 - Oxford 0-15 grading scheme (corneal staining by fluorescein, temporal and nasal staining by lissamine),
 - Van Bijsterveld score (lissamine green staining) / optional examination;
- Schirmer test (without anaesthesia);
- Adverse events;
- Verification of inclusion/exclusion criteria;
- Randomisation.

At investigation sites equipped with Optical Quality Analysing System (OQAS):

- Evaluation of OSI using double pass aberrometry.

For patients with severe Dry Eye, defined as OSDI \geq 33 and/or Corneal Fluorescein Staining \geq 3

- Impression cytology (for HLA-DR).

By **the second investigator** responsible for dispensation:

- Explanations of dosing regimen for IMD;
- IMD dispensation for the period Day 1 to Day 35 according to allocated treatment number.

6.4.3 **Visit #3: Day 8 ± 1 day (optional visit)**

Visit #3 will take place 6 to 8 days after the randomisation visit (visit #2) and can be performed if investigator and/or patient thinks it is necessary.

This visit will consist of the following procedures and examinations (to be done according to the following order and in **each eye** for ocular assessments).

By **the first investigator** in charge of all examinations and safety assessment during the investigation:

- Questioning about concomitant ocular and non-ocular treatment;
- Questioning about AEs between Day 1 and Day 8;
- Measurement of OSDI score;
- Questioning about ocular symptoms;
- Measurement of conjunctival hyperaemia with McMonnies photographic scale;
- Slit lamp examination:
 - TBUT,
 - Oxford 0-15 grading scheme (corneal coloration by fluorescein, temporal and nasal staining by lissamine),
 - Van Bijsterveld score (lissamine green staining) / optional examination;
- Schirmer test (without anaesthesia).

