6.4.4 Visit #4: Day 35 ± 3 days

Visit #4 will take place 35 days ± 3 days after the Randomisation visit (visit #2) and will consist of the following procedures and examinations (to be done according to the following order and in **each eye** for ocular assessments).

By **the first investigator** in charge of all examinations and safety assessment during the investigation:

- Questioning about concomitant ocular and non-ocular treatment;
- Questioning about AEs between Day 1 or Day 8 (optional visit) and Day 35;
- Completion of DEQ-5 questionnaire;
- Measurement of OSDI score;
- Questioning about ocular symptoms;
- Measurement of the far best-corrected visual acuity;
- Measurement of conjunctival hyperaemia with McMonnies photographic scale;
- Urinary pregnancy test (only for childbearing potential women)
- Slit lamp examination with fluorescein and lissamine green stainings for measuring:
 - TBUT,
 - Oxford 0-15 grading scheme (corneal staining by fluorescein, temporal and nasal staining by lissamine),
 - Van Bijsterveld score (lissamine green staining) / optional examination;
- Schirmer test (without anaesthesia);
- Tolerance assessments by the patient and investigator;
- Performance assessment by the investigator;

At investigation sites equipped with Optical Quality Analysing System (OQAS):

- Evaluation of OSI using double pass aberrometry.

By the **second investigator** responsible for dispensation:

- Questioning about AEs between Day 1 or Day 8 (optional visit) and Day 35;
- Questioning about dose regimen compliance;
- Questioning about ocular symptoms upon instillation;
- IMD dispensation for the period Day 35 to Day 84 according to allocated treatment unit number.

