6.4.5 End of investigation visit (visit #5): Day 84 ± 7 days

Visit #5 will take place 84 days ± 7 days after randomisation visit (visit #2) and will consist of the following procedures and examinations (to be done according to the following order and in both eyes for ocular assessments).

By **the first investigator** in charge of all examinations and safety assessment during the investigation:

- Questioning about concomitant ocular and non-ocular treatment;
- Questioning about AEs between Day 35 and Day 84;
- Questioning about ocular symptoms;
- Completion of DEQ-5 questionnaire;
- Measurement of OSDI score;
- Measurement of the far best-corrected visual acuity (Snellen chart);
- Measurement of conjunctival hyperaemia with McMonnies photographic scale;
- Urinary pregnancy test (only for childbearing potential women)
- Slit lamp examination for measuring:
 - TBUT,
 - Oxford 0-15 grading scheme (corneal staining by fluorescein, temporal and nasal staining by lissamine green),
 - Van Bijsterveld score (lissamine green staining) / optional examination;
- Schirmer test (without anaesthesia);
- Tolerance assessment by patient and investigator;
- Performance assessment by investigator;
- Adverse events.

At investigation sites equipped with Optical Quality Analysing System (OQAS):

- Evaluation of OSI using double pass aberrometry.

For patients with severe Dry Eye, defined as OSDI \geq 33 and/or Corneal Fluorescein Staining \geq 3 at baseline visit (Day 1):

- Impression cytology (for HLA-DR).

By the **second investigator** responsible for dispensation:

- Questioning about AEs between Day 35 and Day 84;
- Questioning about dose regimen compliance;
- Questioning about ocular symptoms upon instillation.

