14.1.4 Relationship with the Investigational Medical Device

The investigator will assess the causality/relationship between the IMD and the AE and record that assessment in the e-CRF based on the following definitions (only one answer possible):

1 RELATED: The adverse event is related to the IMD and cannot be reasonably explained by others factor (e.g., concomitant therapy, patient condition, and/or other intervention);

2 NOT RELATED: A simultaneous disease, a simultaneous treatment or any other known cause is clearly responsible for the adverse event.

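### Protocol 6.1 and 6.2.2 assign patient and AE questioning differently, the visit lists follow both, and the masked grader asks unmasked patients about AEs before grading the primary endpoint

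*Protocol*

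**What the plan says.** Section 6.1 explains that the drops look different, so only the investigator is masked. Product identity and instillation data "will not be known by the investigator in charge of the examinations and of performance and safety assessments". It describes the first ophthalmologist as the person "who will be in charge of all examinations and assessments), and patients will be instructed not to disclose drug information".

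Section 6.2.2 says the second "investigator will be in charge of IMD dispensation, accountability and of patient questioning". Under 6.2.3 the dispensing investigator opens the treatment unit, and the box labels in 2.6 name the product.

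The visit lists give the AE question to both people for the same interval:
- Section 6.4.3 (optional Visit 3): "Questioning about AEs between Day 1 and Day 8"
- Section 6.4.4 (Visit 4): "Questioning about AEs between Day 1 or Day 8 (optional visit) and Day 35"
- Section 6.4.5 (Visit 5): "Questioning about AEs between Day 35 and Day 84"

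The procedures are "to be done according to the following order". On causality, Section 14.1.4 says: "The investigator will assess the causality/relationship between the IMD and the AE". It does not say which investigator.

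**The concern.** Patients can identify their product, so the masked grader is the main protection of an observer-read primary endpoint. AE questioning invites the patient to talk about reactions to the drops, and a slip about the product is plausible there. At every follow-up visit the grader has this conversation before he grades staining.

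The plan already recognises the risk elsewhere. Symptoms upon instillation are asked only by the second investigator, and so is regimen compliance at Visits 4 and 5. Tolerance is rated after grading. The grader's AE question can bring out the same reactions but sits near the top of his list.

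There is also a safety-data question. Two people take an AE history for one interval, 14.1.4 does not name the assessor, and no rule was found for reconciling two accounts. The SAP derives adverse device effects from the causality field (3.3) and tabulates related events by arm (6.8.2).

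**Working it through.** The plan states no figure on this point, so the check sets the passages side by side.

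**Step 1: who asks.**

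| Source | First (masked) investigator | Second (product-aware) investigator |
|---|---|---|
| 6.1 | All examinations and assessments, including safety | Dispenses |
| 6.2.2 | Does not dispense or receive returns | Dispensation, accountability, patient questioning |
| 6.4.3 to 6.4.5, AE question | Listed | Listed, same interval |

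The grader's AE question agrees with 6.1 and conflicts with 6.2.2. The dispenser's AE question agrees with 6.2.2 and sits badly with 6.1. The two sections disagree, and the visit lists satisfy both by asking twice.

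**Step 2: when the grader asks.** In each first-investigator list the AE question is item 2. The items between it and Oxford grading are:
- Visit 3: OSDI, ocular symptoms, hyperaemia, TBUT (4 items).
- Visit 4: DEQ-5, OSDI, ocular symptoms, visual acuity, hyperaemia, pregnancy test where applicable, TBUT (7 items, or 6 without the pregnancy test).
- Visit 5: ocular symptoms, DEQ-5, OSDI, visual acuity, hyperaemia, pregnancy test where applicable, TBUT (7 or 6 items).

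The question comes before grading but not immediately before it. The interval does not undo a disclosure once made.

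**Step 3: is a later position workable?** At Visits 4 and 5 tolerance and performance ratings already follow the staining and Schirmer assessments. Visit 5 already ends the first investigator's list with an adverse-events item, in addition to the earlier question. A position after grading therefore exists in the plan.

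**Step 4: who judges causality.** Section 14.1.4 names only the investigator. Section 6.1 and the headings of the first investigator's lists in 6.4.3 to 6.4.5 place safety assessment with the first investigator; the second is described only as responsible for dispensation. Read together, causality belongs to the masked investigator. What is missing is an explicit statement of this, and a rule for an event that the patient mentions only to the dispenser.

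**The case against.** The strongest reply is that a leak is conjecture. An AE question does not ask for product identity, and patients are told not to reveal it. The leaflets in Appendices I and II list overlapping irritation and redness, so event content alone would identify the arm poorly. The grader also asks about concomitant treatments and ocular symptoms before grading, so moving one question cannot seal the mask. All of this stands. It limits the point to one avoidable route; it does not justify keeping the question first.

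A reader might infer three stronger things that the documents do not support.

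- **A measurable inflation of the non-inferiority error.** With SD 2.5 and 38 per group, SE = 2.5 × √(2/38) = 0.574. Suppose 10% to 30% of patients disclose and the grade then shifts by 0.5 to 1 point towards T2259. The bias is 0.10 × 0.5 = 0.05 to 0.30 × 1 = 0.30 point, and the one-sided error at the margin rises from 2.5% to about 3% to 7% (noncentral t, 74 df). The arithmetic is sound, but disclosure rate, shift and direction are all assumed. Nor could the rise be credited to the AE question, since other questions to the same patient also precede grading.
- **Unmasked causality by design.** Nothing gives causality to the dispenser, and 6.1 and the list headings point the other way. This is a wording gap.
- **Double-counted events.** Section 14.1.4 allows one causality answer, and the SAP table notes (7.4.4) count each patient once per SOC and PT, so a duplicate would not inflate patient counts. Discordant entries are possible but not shown.

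**Conclusion.** The point holds as an inconsistency between 6.1 and 6.2.2 that the visit lists carry forward, together with an avoidable order of procedures. Both investigators question the patient about AEs for the same interval at Visits 3 (when held), 4 and 5, and the masked grader does so before Oxford grading. The conclusion rests on the text and on one inference: an unmasked patient describing reactions to the drops may disclose the product despite the instruction. The documents neither show that this happens nor allow any resulting bias to be sized. The change is worth making because it is cheap and follows the plan's own practice of keeping instillation symptoms from the grader and placing tolerance after grading.

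**What to change.** 1. In 6.4.3 to 6.4.5, move the first investigator's AE questioning to after Oxford, Van Bijsterveld (where done) and Schirmer. At Visit 5 the closing adverse-events item can serve, with the earlier question deleted.
2. Reword patient questioning in 6.2.2 so that it agrees with 6.1 and the visit lists, for example by naming the topics the second investigator covers.
3. State in 14.1.4 that the first (masked) investigator assesses severity and causality, once per event. AEs reported only to the second investigator are passed on without product identity.
4. Do not make the second investigator the sole elicitor of AEs. That would let the person who knows the product decide what is reported and how, which gives unmasked judgement more influence on the safety data than it has now.

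The cost is wording, with no extra staff or procedure. The downsides are a short handover note when an AE reaches only the second investigator, and an AE history taken later in the visit. Some exposure remains, because the grader still asks about symptoms before grading.

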6.2.3 Dispensing

The IMD must be dispensed in accordance with the protocol. For each patient included, a treatment kit will be provided and contain enough medication for the whole treatment period.

During the randomisation visit (Day 1), the investigator responsible for IMD dispensation (other than the first ophthalmologist investigator) will open the treatment unit corresponding to the allocated treatment number. Patient numbers must be allocated in an ascending order using the next available consecutive number (to be recorded in the e-CRF). Then, the site team member will provide the patient with the treatment kit to be taken home.

During the whole investigation treatment period, the evaluating ophthalmologist investigator will remain masked to the IMD.

Two dispensations will be performed as follow:

- On Day 1: one box containing enough medication for the treatment period Day 1 to Day 35 will be provided to the patient;
- On Day 35: one box containing enough medication for the treatment period Day 35 to Day 84 will be provided to the patient.

The site team member will instruct patients on the method of instilling the doses.

Patients will be instructed to return unused IMD as well as empty/partially empty containers of used IMD.

A daily record of the IMD containers dispensed to the patient will be maintained by the site team in the Drug Accountability Form.

6.3 Primary and secondary endpoints, with rationale for their selection and measurement

6.3.1 Primary performance endpoint

The primary performance endpoint is change from baseline in total staining grade according to the Oxford 0-15 grading scheme (corneal staining by fluorescein, nasal and temporal conjunctival staining by lissamine green) at D35 in the worst eye.

6.3.2 Secondary performance endpoints

Secondary performance endpoints are:

- Change from baseline in total ocular staining grade according to Oxford grading scheme at Day 8 and Day 84 in the worst eye and at Day 8, Day 35 and Day 84 in the contralateral eye;
- Change from baseline in Van Bijsterveld score* (lissamine green staining) / optional examination at Day 8, Day 35 and Day 84;
- Change from baseline in DEQ-5 at Day 35 and Day 84 ;
- Change from baseline in OSDI (Ocular Surface Disease Index) score at Day 8, Day 35 and Day 84;
- Change from baseline in Schirmer test result* (without anaesthesia) at Day 8, Day 35 and Day 84;
- Change from baseline in TBUT* (Tear Break-Up Time) at Day 8, Day 35 and Day 84 ;
- Conjunctival hyperaemia* using McMonnies photographic scale at Day 8, Day 35 and Day 84;
- HLA-DR (AUF) at Day 84 in Right Eye if eligible eye;
- Objective Scatter Index (OSI) at Day 35 and Day 84;
- Dry Eye symptoms: burning/irritation, stinging/eye pain, itching, eye dryness feeling, foreign body sensation, light sensitivity and fluctuating blurred vision evaluated with a 4-level verbal scale (0 = Absent; 1 = Mild, Present but not disturbing; 2 = Moderate, Disturbing, but not limiting daily activities; 3 = Severe, Very distressing and interfering with daily activities) and change from baseline in total score of Dry Eye symptoms at Day 8, Day 35 and Day 84;
- Performance assessment by the investigator (Unsatisfactory, Not very satisfactory, Satisfactory, Very satisfactory) at Day 35 and Day 84.

*Assessment recorded for each eye will be analysed for the worst eye and the contralateral eye.

6.3.3 Safety endpoints

Other evaluation parameters are:

- Ocular symptoms upon instillation at Day 8, Day 35 and Day 84: Burning/irritation, stinging/eye pain, itching, eye dryness feeling, foreign body sensation, light sensitivity and other symptoms will be graded by the subject according to the

following severity scale and with their duration: (0 = Absent; 1 = Mild, Present but not disturbing; 2 = Moderate, Disturbing, but not limiting daily activities; 3 = Severe, Very distressing and interfering with daily activities);

- Far best-corrected visual acuity (in logMAR) at Day 84;
- Tolerance assessment by the patient and the investigator (Unsatisfactory, Not very satisfactory, Satisfactory, Very satisfactory) at Day 35 and Day 84 ;
- Ocular and systemic adverse events (ADE/SADE).

These endpoints have been chosen considering the clinical literature review of Thealoz Duo® (Pinto-Bonilla et al. 2015; Schmidl et al. 2015; Schmidl et al. 2016-abstract; Chiambaretta et al. 2017). They are clinically relevant, clearly defined and assessed at a specified time point in order to provide clinical evidence on the performance and tolerance of the T2259 device in the target population for the management of the ocular signs and symptoms of patients with dry eye disease.

6.4 Methods and timing for assessing, recording, and analysing variables

Five visits are scheduled during the course of the investigation as presented below:

- Visit #1: selection visit (between day 1 -10 and day 1 -7);
- Visit #2: randomisation visit (day 1);
- *Visit #3: day 8 ± 1; Optional visit (if the investigator and/or the patient thinks it is necessary)*
- Visit #4: day 35 ± 3 days;
- Visit #5: final visit (day 84 ± 7 days).

Visits V2, V3, V4 and V5 should be performed at the same hour (± 4 hours). Investigations are to be conducted as per the schedule of investigation procedures detailed in [Table 2](#), page [12](#).

6.4.1 Selection visit (visit #1): Day 1 -10 days/Day1 -7 days

Preliminary remark: Informed consent

The patient (or/and the legally acceptable representative) must be verbally informed about the investigation and must be given a copy of the patient information sheet. The patient (or/and the legally acceptable representative) must be given the opportunity to ask questions, and have reasonable time for reflection before giving his/her informed consent.

Written informed consent must be obtained prior to initiation of any investigational procedures or any discontinuation of current medication. No measures whatsoever described in the CIP shall be undertaken without such consent indicating that the patient (or/and the legally acceptable representative) has been given both verbal and written information about the investigation and the IMD.

The informed consent form shall be signed and dated by the patient (or/and the legally acceptable representative) and the investigator or a physician designated by the investigator. Two original consent forms will be signed and one shall be included in the investigator's

investigation file, the other one shall be given to the patient (or/and the legally acceptable representative).

Visit #1 will consist of the following procedures and examinations to be done according to the following order and in each eye for ocular assessments.

By **the investigator** in charge of all examinations and safety assessment during the investigation:

- Information of the patient and signature of the informed consent;
- Demography;
- Questioning about ocular medical and surgical history;
- Questioning about systemic medical and surgical history;
- Questioning about previous and concomitant ocular and non-ocular treatments;
- History of Dry Eye;
- Completion of DEQ-5 questionnaire;
- Questioning about ocular symptoms;
- Measurement of the far best-corrected visual acuity;
- Measurement of conjunctival hyperaemia with McMonnies photographic scale;
- Urinary pregnancy test (only for childbearing potential women)
- Slit lamp examination for measuring:
 - TBUT,
 - Oxford 0-15 grading scheme (corneal coloration by fluorescein, temporal and nasal staining by lissamine),
 - Van Bijsterveld score (lissamine green staining) / optional examination;
- Verification of inclusion/exclusion criteria;
- Dispensation of Hydrabak® for the run-in period.

6.4.2 Randomisation visit (visit #2): Day 1

Visit #2 will take place 7 to 10 days after the selection visit (visit #1) and will consist of the following procedures and examinations (to be done according to the following order and in **each eye** for ocular assessments).

By **the first investigator** in charge of all examinations and safety assessment during the investigation:

- Questioning about Hydrabak® compliance during the run-in period;
- Questioning about concomitant ocular and non-ocular treatments;
- Questioning about AEs during the run-in period;
- Measurement of OSDI score;
- Questioning about ocular symptoms;
- Measurement of conjunctival hyperaemia with McMonnies photographic scale;
- Slit lamp examination for measuring:
 - TBUT,
 - Oxford 0-15 grading scheme (corneal staining by fluorescein, temporal and nasal staining by lissamine),
 - Van Bijsterveld score (lissamine green staining) / optional examination;
- Schirmer test (without anaesthesia);
- Adverse events;
- Verification of inclusion/exclusion criteria;
- Randomisation.

At investigation sites equipped with Optical Quality Analysing System (OQAS):

- Evaluation of OSI using double pass aberrometry.

For patients with severe Dry Eye, defined as OSDI \geq 33 and/or Corneal Fluorescein Staining \geq 3

- Impression cytology (for HLA-DR).

By **the second investigator** responsible for dispensation:

- Explanations of dosing regimen for IMD;
- IMD dispensation for the period Day 1 to Day 35 according to allocated treatment number.

6.4.3 **Visit #3: Day 8 ± 1 day (optional visit)**

Visit #3 will take place 6 to 8 days after the randomisation visit (visit #2) and can be performed if investigator and/or patient thinks it is necessary.

This visit will consist of the following procedures and examinations (to be done according to the following order and in **each eye** for ocular assessments).

By **the first investigator** in charge of all examinations and safety assessment during the investigation:

- Questioning about concomitant ocular and non-ocular treatment;
- Questioning about AEs between Day 1 and Day 8;
- Measurement of OSDI score;
- Questioning about ocular symptoms;
- Measurement of conjunctival hyperaemia with McMonnies photographic scale;
- Slit lamp examination:
 - TBUT,
 - Oxford 0-15 grading scheme (corneal coloration by fluorescein, temporal and nasal staining by lissamine),
 - Van Bijsterveld score (lissamine green staining) / optional examination;
- Schirmer test (without anaesthesia).

By **the second investigator** responsible for dispensation:

- Questioning about AEs between Day 1 and Day 8,
- Questioning about ocular symptoms upon instillation.

